14.1.3. Secondary Analyses

All secondary outcomes will be evaluated using the ITT population and GEE methodology. Systemic outcomes that are only applicable to a particular comorbid disease subgroup will only be evaluated in that population. Specifically, flow-mediated dilation and Carotid intima media thickness (IMT) will be evaluated in all subjects.

14.1.4. Exploratory Analyses

Among those who meet all initial screening criteria and receive an oral health screening, we will analyze the prevalence and severity (Stage I, II, III) of periodontal disease, overall and by subgroups of interest (e.g., demographic characteristics, comorbidity disease category, etc.). Other details of exploratory analyses may be described in the Statistical Analysis Plan.

14.2. Sample Size and Power

This study is powered to detect a mean reduction in periodontal probing depth of 0.88 (SD 0.5) mm over the course of 12 months of periodontal therapy in the Treated group, versus a mean reduction of 0.63 (SD 0.59) mm in the Control group. Assuming a 2-tailed test with $\alpha = 0.05$, we need 200 subjects (100 per group) to have 90% power to achieve statistical significance. Assuming a 10% drop out during the study, this means we need to recruit approximately 200 - 224 subjects (112 per Control and Treatment group). If the dropout rate is found to be greater than 10%, additional recruitment may be required to achieve the target of approximately 100 - 112 per group.

For the correlation analyses, we can assume various distributions of prediabetes, type 2 diabetes, and cardiovascular disease among the study cohort (note that subjects may qualify for more than one category). Given the total sample size of 224, the table below describes the effect sizes (i.e., Pearson correlation coefficients) this study would have the power to detect with various cohort distributions and power levels.

Correlations able to be detected in a subgroup, by sample size and power

| | Cohort representation, out of overall study population, N = 224 | | | |
|-------|---|-------------|-------------|--------------|
| Power | 1/6, N = 37 | 1/4, N = 56 | 1/3, N = 75 | 1/2, N = 112 |
| 70% | 0.422 | 0.346 | 0.300 | 0.247 |
| 80% | 0.468 | 0.386 | 0.336 | 0.277 |
| 90% | 0.528 | 0.439 | 0.384 | 0.317 |

Note: $\alpha = 0.0$

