1.3. Summary of Research Plan

The Baseline Oral Health Study will enroll approximately 200 participants in the study with approximately 100 participants each within the Control Group and the Treatment Group. The study population will be recruited from the Project Baseline Health Study participants in the North Carolina region and may be expanded to include subjects recruited outside of the Project Baseline Health Study if the initial screening from the Project Baseline Health Study pool of participants in the North Carolina region does not fulfill study enrollment powering. Screening methods for eligible participants may include review of electronic health records (EHR) or other systems in compliance with local requirements. The participants enrolled in the study will then be randomized into a Control Group and Treatment Group. The screened participants that become eligible and consented to this study will be seen at dental health sites. UNC study team will be the Principal Investigating team for this protocol.

The periodontal disease study will be presented to eligible participants and those interested will be scheduled for a screening visit (S0). (See Figure 1). At the screening visit, participants will be consented and provided with an oral health assessment, initial X-Ray series (Full Mouth series and vertical bitewings) per standard of care, a point of care blood glucose test and will be scheduled to receive Screening Visit flow mediated dilation (FMD) and carotid intima media thickness (IMT) measurements. Those meeting in/ex criteria will be enrolled into the study and a Screening Visit 1 (S1) will be scheduled for those subjects who need hopeless teeth extracted. A Screening Visit 2 (S2) may be scheduled as a post-operative visit or to extract additional hopeless teeth depending on allotted time available for the Screening Visit visit 1 (S1). The subjects will additionally be scheduled for the Baseline visit (T0, see Figure 1). The Screening Visits should be scheduled to take place no later than 2 weeks before the scheduled Baseline visit.

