14.1.2. Primary Analyses

Analyses associated with the first primary outcome, the impact of treatment on oral health measures, will be performed using generalized estimating equations (GEE) methods. Longitudinal outcomes in the Treated vs. Control groups will be compared and will include all subjects who were randomized and their data from visits T1 - T4 based on intent-to-treat (ITT) group assignment.

The second primary outcome, association between changes in oral health and changes in systemic health, will be evaluated using correlation analysis. Changes in the measures of oral and systemic health between Baseline (T0) and follow-up visit 4 (T4) will be calculated for all subjects in the study who complete the T4 visit. The strength of correlations between changes in oral health and change in HbA_{1c} (in subjects with prediabetes or type 2 diabetes) or change in flow mediated dilation will be evaluated.

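### Enrolling 200, as Section 1.3 and the lower end of Section 14.2's range allow, leaves no room for the assumed 10% dropout, and the correlation table's N labels do not match its values

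*Combined protocol and SAP*

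**What the plan says.** Section 14.2 sizes the trial on the probing-depth comparison. It is "powered to detect a mean reduction in periodontal probing depth of 0.88 (SD 0.5) mm" in the Treated group against 0.63 mm (SD 0.59) in the Control group, two-tailed at alpha 0.05, and it states that "we need 200 subjects (100 per group) to have 90% power to achieve statistical significance". It then assumes 10% dropout and says "this means we need to recruit approximately 200 - 224 subjects (112 per Control and Treatment group". On later top-up it says "If the dropout rate is found to be greater than 10%, additional recruitment may be required", to reach about 100 to 112 per group.

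Section 1.3 says that the study "will enroll approximately 200 participants in the study with approximately 100 participants each within the Control Group and the Treatment Group".

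For the correlations, Section 14.2 says "Given the total sample size of 224, the table below describes the effect sizes". The table that follows has columns for one sixth, one quarter, one third and one half of 224, labelled N = 37, 56, 75 and 112, and rows for 70%, 80% and 90% power.

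Section 14.1.2 defines who is analysed. The treatment comparison is a GEE that "will include all subjects who were randomized and their data from visits T1 - T4", by assigned group. The changes used in the correlation analysis "will be calculated for all subjects in the study who complete the T4 visit".

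**The concern.** There are two linked problems.

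1. The plan carries two enrolment targets. The 200 in Section 1.3 and at the lower end of the Section 14.2 range equals the plan's own requirement before any dropout. If dropout is exactly the assumed 10%, the top-up clause is not triggered, and the trial can finish with 180 completers without departing from the plan.

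2. The table's printed correlations do not reproduce at the printed N. A reader cannot tell whether N means enrolled or evaluable.

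Both primary outcomes are affected. The stated 90% power for probing depth and the printed detectable correlations each need about 200 evaluable subjects, which means about 224 randomised under the plan's own dropout assumption.

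**Working it through.** **Inputs (Section 14.2).** Reductions of 0.88 and 0.63 mm (difference 0.25), SDs 0.5 and 0.59, two-sided alpha 0.05, 90% power, 10% dropout. Allocation is 1:1 (Section 1.3).

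**Step 1: the plan's own number.**
n per group = (1.960 + 1.2816)² × (0.5² + 0.59²) / 0.25² = 10.508 × 0.5981 / 0.0625 = 100.6.
This agrees with the stated 100 per group. Hence 200 is the evaluable number, before dropout.

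**Step 2: dropout.**
100 / 0.90 = 111.1, rounded up to 112 per group, or 224 in total. This matches the upper end of the range and the bracketed figure. Nothing in the calculation yields 200 after dropout.

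**Step 3: power for each enrolment figure (completers only).**
Normal approximation: power = Φ(0.25 / √(0.5981/n) − 1.960). The t column uses the noncentral t distribution with unequal variances.

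| Scenario | n per group | Power, t | Power, normal |
|---|---|---|---|
| 200 evaluable | 100 | 89.6% | 89.8% |
| 200 enrolled, 10% lost (180) | 90 | 86.2% | 86.6% |
| 224 enrolled, 10% lost (201.6) | 100.8 | 89.8% | 90.1% |

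The shortfall at 200 enrolled is 89.6 − 86.2 = 3.4 points (t), or 3.6 points against the 224 scenario.

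**Step 4: N implied by the correlation table.**
The alpha note under the table is cut off in the text available, so two-sided 0.05 is assumed. By Fisher z, detectable r = tanh((1.960 + z_power) / √(N − 3)). Inverted, N = ((1.960 + z_power) / atanh(r))² + 3.
Example: r = 0.468 at 80% power gives atanh(r) = 0.5075, and (2.8016 / 0.5075)² + 3 = 33.5.

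| Row | Labelled 37 | Labelled 56 | Labelled 75 | Labelled 112 |
|---|---|---|---|---|
| 70% | 33.5 | 50.4 | 67.4 | 100.0 |
| 80% | 33.5 | 50.4 | 67.2 | 100.0 |
| 90% | 33.5 | 50.4 | 67.1 | 100.5 |

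224 less 10% is 201.6, and its sixth, quarter, third and half are 33.6, 50.4, 67.2 and 100.8. Over the 12 cells, the root-mean-square difference from the printed r is 0.0006 for these N, 0.0011 for fractions of 200, and 0.0184 for the labelled N.

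**Step 5: detectable r at 80% power on each basis.**

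| Basis | 1/6 | 1/4 | 1/3 | 1/2 |
|---|---|---|---|---|
| Printed | 0.468 | 0.386 | 0.336 | 0.277 |
| Labelled N (37/56/75/112) | 0.447 | 0.367 | 0.319 | 0.262 |
| 224 less 10% (33.6/50.4/67.2/100.8) | 0.467 | 0.386 | 0.336 | 0.276 |
| 200 less 10% (30/45/60/90) | 0.492 | 0.407 | 0.355 | 0.292 |

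**Step 6: power of the printed r with 200 enrolled and 10% lost.**
Power = Φ(atanh(r) × √(N − 3) − 1.960) at N = 30/45/60/90. The row marked 70% has 64.7–65.3%, the row marked 80% has 75.1–75.6%, and the row marked 90% has 86.3–86.5%.

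**Step 7: could another alpha rescue the labels?** No. At the labelled N, the 80% row would be 0.484/0.400/0.348/0.287 for two-sided 0.025 and 0.527/0.438/0.382/0.316 for 0.01. One-sided 0.05 implies N of about 27/40/54/79. Solving for alpha at the labelled N gives about 0.036 in the 70% row and 0.032 in the 90% row, so no single alpha fits.

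**The case against.** The best case for the plan is that this is loose wording. Section 14.2 does the dropout calculation correctly and prints 112 per group, and its range can be read as running from evaluable to recruited. Section 1.3 is a summary, says approximately, and allows recruitment from outside the Baseline Health Study if the first pool does not meet the powering need. The 86% belongs to a completers-only test, whereas the planned GEE keeps the T1–T4 data of subjects who leave early. The column labels are correct fractions of 224, the printed correlations are right for 224 enrolled, and at the labelled N they would have more power than stated (about 75%, 84% and 93%). The cohort fractions are illustrative. The flow-mediated dilation correlation is not restricted to a disease subgroup, so no single column governs it.

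Much of this stands as a limit on size. The power loss is modest, 86% is a completer-basis figure, and the table errs on the cautious side if 224 are enrolled.

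It does not remove the inconsistency. The range is worded as the number to recruit, and Section 1.3 gives about 100 per group as enrolment. The provision for wider recruitment concerns where subjects come from and does not change the number. Partial follow-up does not help the correlations, which use T4 completers only. The table is titled by sample size and never says that its values are net of dropout.

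**Conclusion.** The concern holds on both parts. The 200 in Section 1.3 and at the lower end of the Section 14.2 range has no dropout allowance. At the assumed 10% dropout it gives 86.2% (t) or 86.6% (normal) power for probing depth, against 89.6% or 89.8% at 100 per group. This is a completers-only figure, and the GEE's loss may be smaller.

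The correlation table's N labels do not match its values, which correspond to 224 enrolled less 10%. The values are usable if 224 are enrolled. With 200 enrolled, the detectable correlations at 80% power rise to 0.492/0.407/0.355/0.292. The table result assumes two-sided alpha 0.05 and the Fisher z approximation.

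The plan should be corrected on both points. The effect on power is moderate and does not invalidate the design.

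**What to change.** Use one enrolment target in Sections 1.3 and 14.2, by one of two routes:

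- **Target 224.** State 224 randomised (112 per group) in both places and delete the lower end of the range. The stated 90% and the printed correlations then stand.
- **Keep 200.** Restate the probing-depth power as about 86% on a completer basis, noting that the GEE also uses partial follow-up. Reprint the correlations for 30/45/60/90 completers (80% power: 0.49/0.41/0.36/0.29).

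In either case, label the table columns with the evaluable N used, and state that it is net of 10% dropout.

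The cost is restated figures in two sections and relabelled columns. Keeping 200 changes nothing in conduct. Targeting 224 means up to 24 more participants than Section 1.3 states.
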